## ABSTRACT

**Objectives:** To investigate the effectiveness of AcceleDent Aura vibrating device on rate of canine retraction. **Materials and Methods:** Thirty-two patients requiring extraction of upper first premolars and canine retraction were randomly allocated with a 1:1 ratio into either no-appliance group or the AcceleDent Aura appliance group. Canine retraction was done applying 150gm of retraction force using NiTi coil springs on 16\*22 stainless steel archwires. The duration of the study was 4 months. Digital models were obtained directly after extraction of upper first premolars and at monthly intervals during canine retraction for recording the monthly as well as the total distance moved by the canine. Digitized models were superimposed on the initial model and data were statistically analyzed. Anchorage loss, rotation, tipping, torque and root condition were evaluated using cone beam computed tomography imaging. Pain was evaluated by visual analog scale. **Results:** No patients were dropped-out during this study. There was no statistically significant difference between both groups regarding the total distance travelled by the canine ( $P=0.436$ ), as well as the rate of canine retraction per month ( $P=0.17$ ). Regarding the pain level, there was no statistically significant difference between the two groups at day 0 ( $P=0.721$ ), after 24 hrs. ( $P=0.882$ ), after 72 hrs. ( $P=0.378$ ) and after 7 days ( $P=0.964$ ). **Conclusion:** AcceleDent Aura was not able to accelerate orthodontic tooth movement. Pain level couldn't be reduced by vibrational force

with an AcceleDent device during orthodontic treatment. Root condition was not affected by the vibrational forces.

**KEY WORDS:** AcceleDent; Acceleration of tooth movement; Vibrating devices; Canine retraction; Digital models

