## INTRODUCTION

Shortening of the treatment time via accelerating orthodontic tooth movement (OTM) continues to be a relentless challenge and demand in the mainstream orthodontics. To date, several modalities have been investigated to accelerate OTM through mechanical, pharmacological, surgical and physical approaches.

Vibrating devices are another example of physical acceleration of OTM. AcceleDent vibrating device (OrthoAccel Technologies, Houston, Texas) has been introduced to the market in 2009. It was intended to be used by the patients in conjunction with fixed orthodontic appliances or aligners, for 20 minutes per day. It vibrates at a frequency of 30Hz and has a force amplitude of 20 grams. The mechanism of action is hypothesized to be via enhancing bone remodelling through increased RANKL expression together with elevation in IL-1 beta levels with a result in rise of the rate of tooth movement after application of vibration in humans

and mice, respectively. The results reported in the literature concerning the efficiency of these devices in acceleration of tooth movement are controversial.

The aim of this study was to investigate the effectiveness of AcceleDent Aura vibrating device on the rate of canine retraction. The null hypothesis was that there is no difference in the rate of canine retraction between AcceleDent Aura appliance group and no appliance group. Other side effects including pain and root resorption were also considered.

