### **Sample Size Calculation**

The sample size for the current study was calculated based on the results of Kau et al. A total sample size of 52 canines was calculated to detect a large effect size ( $d=0.8$ ) with 80% power and 5% significance level. This number has been increased to a total sample size of 64 canines to count for the expected sample attrition. The outcome variable is normally distributed. The sample size was calculated using G-Power program (University of Düsseldorf, Düsseldorf, Germany).

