## **Cone beam Computed Tomography**

Pre- and post-retraction CBCT images were obtained for each patient using the same CBCT machine with the following parameters: Resolution (Voxel size): 0.3\0.3 mm, exposure time: 10-20 sec, Anode voltage: 57-90 kV, field of view (FOV): 6×8 cm limited to the maxilla, and anode current: 4-16 mA. A total of 36 CBCT images were obtained at the end of the study (18 pre-retraction and 18 post-retraction) upon which the analysis was done.

The DICOM files obtained from the imaging centre were manipulated using In vivo 5 (Anatomage) version 5.3 software to perform the CBCT measurements as follows: Landmarks (Table 2), reference lines/planes (Table 3) (Figure 4) and measurements (Table 4) were all recorded in their corresponding modules. Then, an analysis was created and saved to be used for all pre- & post-retraction CBCT images.

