## **Statistical Analysis**

Data management and statistical analysis were done using Statistical Package

for Social Sciences, Version 21.0 (SPSS Inc., Chicago III) for Windows. Shapiro-Wilk tests of normality were used to test normality of all quantitative variable distributions. Canine retraction in millimetres was presented as mean and standard deviation (SD). Kruskal-Wallis test was used to test the difference in the incremental rate of retraction between the two groups. Independent t-test was used to determine the statistical differences in the total distance travelled.  $P$ -value  $<0.05$  was considered statistically significant. All tests were two-sided. Concordance correlation coefficients (CCCs) were calculated to detect the intra- and inter-examiner reliability of the measurements.

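### The abstract concludes no effect on movement, pain and roots from non-significant P-values (none for roots), and the statistical section names no confidence interval for any group difference

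*Combined protocol and SAP*

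**What the plan says.** The Conclusion of the Abstract makes three categorical statements: "AcceleDent Aura was not able to accelerate orthodontic tooth movement"; "Pain level couldn't be reduced by vibrational force"; and "Root condition was not affected by the vibrational forces". The Results part of the Abstract gives P=0.436 for total distance, P=0.17 for monthly rate, and P=0.721, 0.882, 0.378 and 0.964 for pain at day 0, 24 hours, 72 hours and 7 days. It gives no group difference, direction or interval for any of these, and nothing at all for roots.

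The Introduction sets an ordinary superiority framework: "The null hypothesis was that there is no difference in the rate of canine retraction" between the groups. No equivalence or non-inferiority margin appears. Under Sample Size Calculation, "A total sample size of 52 canines was calculated to detect a large effect size" (d=0.8, 80% power, 5% level), later raised to 64 canines.

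The Statistical Analysis section lists means and SDs for canine retraction, a Kruskal-Wallis test for rate, and for distance: "Independent t-test was used to determine the statistical differences in the total distance travelled". It names no confidence interval for a group difference, and no test for pain or root length.

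On the scans behind the root conclusion, the CBCT section says: "A total of 36 CBCT images were obtained at the end of the study (18 pre-retraction and 18 post-retraction". The Abstract reports 32 patients randomised and none lost.

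**The concern.** A non-significant test of no difference means that the data did not rule out zero. It does not mean that they ruled out a useful effect. To conclude that a device does not work, or does no harm to roots, the reader needs an interval narrow enough to exclude effects that matter. The text supplied neither reports such an interval nor plans one.

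The Introduction calls the existing evidence on these devices controversial, so a reader will want the size and precision of the effect more than a verdict. The root statement is the weakest of the three. It is a reassurance about a possible harm, it has no figure behind it in the Abstract, and the scan count suggests that it may rest on little more than half of the randomised patients.

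**Working it through.** **Inputs.** From the documents: d=0.8 per canine, two-sided 5% level, 52 then 64 canines, 32 patients allocated 1:1 (taken as 16 per arm, two canines each), the P-values above, and 18 scan pairs. Assumed: within-patient correlation between the two canines (ICC) of 0.2 / 0.5 / 0.8; d=0.5 as an illustrative moderate effect, which no document calls important; one scan pair per patient, split 9 v 9. All effects are in SD units because the Abstract gives no means or SDs.

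**The plan's own figure.** A two-sided two-sample t-test for d=0.8 with 80% power needs 25.52, so 26 per arm and 52 in total (power 80.7%). The stated 52 reproduces and is not in dispute.

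**Power at the achieved size, in canine SD.** The plan defines d on canines. The mean of two canines has SD √((1+ICC)/2) canine SD, so a canine-level d becomes d/√((1+ICC)/2) with 16 v 16 patients.

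| Effect | 64 independent canines | Patient means, ICC 0.2 / 0.5 / 0.8 |
|---|---|---|
| d=0.8 | 88% | 81% / 72% / 64% |
| d=0.5 | 50% | 42% / 35% / 30% |

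**Total distance, P=0.436, taken as a canine-level t-test.**
- t(62) = 0.784, so |d| = 0.784 × √(2/32) = 0.196.
- Independent canines: half-width = 1.999 × 0.25 = 0.500.
- Allowing for pairing: SE = √((1+ICC)/2 × 2/16) = 0.274 / 0.306 / 0.335. With 30 df, half-width = 2.042 × SE = 0.559 / 0.625 / 0.685.
- The upper limit for device benefit is half-width + 0.196 if the device was ahead, and half-width − 0.196 if control was ahead.

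| | Independent | ICC 0.2 / 0.5 / 0.8 |
|---|---|---|
| Device ahead | 0.70 | 0.76 / 0.82 / 0.88 |
| Control ahead | 0.30 | 0.36 / 0.43 / 0.49 |

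**Monthly rate, P=0.17.** This comes from a rank test, so no interval is derived.

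**Pain, assuming a t-type test with 16 per arm.** Half-width = 2.042 × √(2/16) = 0.722. The |d| values are 0.127, 0.053, 0.316 and 0.016. Whichever arm was ahead, the interval reaches at least half-width − |d| of benefit:
- day 0: 0.722 − 0.127 = 0.59 (0.595 before rounding)
- 24 h: 0.722 − 0.053 = 0.67
- 72 h: 0.722 − 0.316 = 0.41
- 7 days: 0.722 − 0.016 = 0.71

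Three of the four exceed 0.5.

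**Roots, 9 v 9 patients assumed.** There is no P-value to convert, so only precision can be gauged. With 18 v 18 independent canines, half-width = 2.032 × √(2/18) = 0.68. With patient means (16 df), half-width = 2.120 × √((1+ICC)/2 × 2/9) = 0.77 / 0.87 / 0.95 canine SD.

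**The case against.** **The results are not visible.** The supplied text stops at Statistical Analysis. A results section may hold group differences, intervals and root figures. A reader might infer that none were calculated; the documents do not show that. This stands, and it confines the point to the Abstract's wording and the methods text. The Results part of the Abstract is itself properly worded; only its Conclusion goes too far.

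**The movement claim is one-directional.** If control was ahead, every scenario above puts the upper limit for device benefit below 0.5 SD. A reader might infer that a moderate benefit was probably missed; without the direction, that does not follow. What stands is that the Abstract withholds the fact that would settle it.

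**Units matter.** A reader might apply d=0.8 and d=0.5 to 16 v 16 patients and obtain 59% and 28% power. Those are patient-mean SDs and equal the plan's canine-level effect only if the two canines carry identical information (ICC of 1). The canine-scale figures above are the fair ones.

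**Pain may also have been rank-tested.** No test is named for it, so the pain limits are conditional on a t-type test and carry less weight than the wording point.

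**Neighbouring issues.** Pairing of canines, the scan count and the unnamed tests are separate defects. They enter here only because they affect how wide an honest interval would be.

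**Conclusion.** The point holds and should be acted on. Confidence is high that the three conclusions go beyond what the Abstract and methods text can support, most clearly for roots. Confidence in the size is lower:

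- **Total distance:** whether a 0.5 SD benefit is excluded depends on the unreported direction, and the limits assume a canine-level P-value and an ICC the documents do not give.
- **Rate**, the outcome in the stated aim: not quantified here.
- **Pain:** a 0.5 SD reduction remains open at three of four reported times, if the tests were t-type with 16 per arm.
- **Roots:** the half-width of 0.68 to 0.95 SD assumes one scan pair per patient and a 9 v 9 split.

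None of this shows that the device works or harms roots, and the sample-size figure is not wrong. It shows that the text supplied does not demonstrate absence of effect.

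**What to change.** Add to Statistical Analysis, labelled as a post hoc addition because Trial Design says that the methodology did not change after commencement:

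*For each outcome we report the between-group difference, its direction, its 95% confidence interval and the number of patients analysed: rate (mm/month; Hodges-Lehmann or bootstrap interval if not normal), total distance (mm), pain VAS at each recorded time including 48 hours, and change in apex-to-cusp length (mm). Intervals for canine outcomes allow for two canines per patient, for example by using the patient mean.*

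Reword the movement and pain conclusions:

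*No statistically significant difference was detected; a difference up to [CI limit] in favour of the device is not excluded.*

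Reword the root conclusion:

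*In [n] patients with CBCT, the difference in root length change was [estimate]; a harmful difference up to [CI limit] mm is not excluded.*

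If the results section already holds these estimates, carry them into the Abstract, after checking that the canine intervals allow for pairing.

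Cost: two sentences of methods, a re-analysis of existing data and three reworded conclusions. The conclusions become weaker, and reported P-values may change once pairing is allowed for.

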## **Measurements used in the CBCT Analysis**

Measurements of the total distance of canine retraction, the canine tipping, torque and rotation were analysed by measuring the angles between the long axis lines for the canines and the three reference planes were measured to detect tipping and torque movements. Also, the angle between the horizontal line of the first molar and the sagittal plane to detect canine rotation.

For assessment of root resorption, the axial guided navigation method explained by Castro et al and Schwartz et al was used. Using the software In-vivo 5, version 5.3(Anatomage, Inc., Santa Clara, CA 95054, USA). the pre- & post-retraction CBCTs obtained for each patient were used to evaluate the effect of AcceleDent on root resorption, the linear length between the root apex and cusps tip was measured.

The evaluation was carried by two blinded examiners. In order to fully visualize the root, the CBCT image was re-oriented on each root so that the cross-section would pass through the long axis of each canine (Figure 5).

The degree of pain was measured by Visual Analog Score (VAS), these charts were filled by the patients for the following week after beginning of canine retraction at time intervals (0, 24 hours , 48 hours, 72 hours and 7 days ) and were gathered at the end of the week. The pain VAS was in the format of a chart that contained a series of 10-cm horizontal scales on which the patient marked the degree of pain (0 to 10, where 0 refer to no pain and 10 refer to sever pain) at the indicated time periods.

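### The CBCT count (36 images) conflicts with scanning every one of 32 patients, and on either count the flat conclusion that roots were unaffected is not supported

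*Combined protocol and SAP*

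**What the plan says.** The Introduction lists root resorption among the side effects considered. The Abstract gives 32 patients randomised 1:1 and no drop-outs, and ends its conclusion with "Root condition was not affected by the vibrational forces". Its Results sentences give P values for distance, rate and pain, and no figure for roots.

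The Cone beam Computed Tomography section makes two statements about who was scanned:

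- "Pre- and post-retraction CBCT images were obtained for each patient using the same CBCT machine"
- "A total of 36 CBCT images were obtained at the end of the study (18 pre-retraction and 18 post-retraction", after which the sentence says that these images were the ones analysed.

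The section on CBCT measurements repeats the first statement: the "CBCTs obtained for each patient were used to evaluate the effect of AcceleDent on root resorption". For the root reading it names a method from cited work ("For assessment of root resorption, the axial guided navigation method") and then describes one quantity: "the linear length between the root apex and cusps tip was measured". Its orientation is given as "the CBCT image was re-oriented on each root so that the cross-section would pass through the long axis of each canine".

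The Statistical Analysis section names a test for the incremental rate and one for the total distance. It names no test, estimate or interval for the root reading. The Sample Size Calculation is not tied to a root outcome.

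**The concern.** The two statements about scanning cannot both be right. If every patient had a scan before and after, there should be 64 images. If 36 is right, 14 patients have no pair, and nothing in the document describes a planned CBCT subset, how it was chosen, or how it fell between the arms. A comparison on a subset selected in an unstated way no longer has the plain protection of the randomisation.

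The conclusion then says more than a group of this size can show. To say that roots were unaffected is to say that absence of an effect was demonstrated. With at most 32 patients, and apparently 18, a non-significant comparison leaves a broad range of differences open. Someone reading only the Abstract would take root safety as established, and would see neither the number of patients nor the range of root shortening still compatible with the data.

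**Working it through.** **Step 1. The image count.** Inputs: 32 patients and no drop-outs (Abstract); one scan before and one after for each patient, and the stated 36 images (Cone beam Computed Tomography).

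- The stated count agrees with itself: 18 + 18 = 36, or 36 / 2 = 18 pairs.
- Expected if every patient was scanned twice: 32 × 2 = 64.
- Unaccounted for: 64 − 36 = 28 images, or 28 / 2 = 14 patients.
- Coverage at one pair per patient: 18 / 32 = 56%.

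**Step 2. What each count can show.** The root data and their SD are not given, so the result is in units of the SD of one value per patient (change in length, left and right canines averaged).

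Half-width of the 95% interval = t(0.975, n1 + n2 − 2) × √(1/n1 + 1/n2)

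| Patients per arm | t | √(1/n1 + 1/n2) | Half-width (SD) |
|---|---|---|---|
| 9 / 9 (assumed even split of 18) | 2.120 | 0.471 | 1.00 |
| 6 / 12 (assumed uneven split of 18) | 2.120 | 0.500 | 1.06 |
| 16 / 16 (all 32 scanned) | 2.042 | 0.354 | 0.72 |

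**Step 3. The unit matters.** Averaging two canines with within-patient correlation r multiplies the per-canine SD by √((1 + r)/2): 0.707 at r = 0, 0.866 at r = 0.5, and 1 at r = 1. In per-canine SD units the half-widths are therefore:

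- 9 / 9: 0.71 (r = 0), 0.87 (r = 0.5), 1.00 (r = 1)
- 16 / 16: 0.51, 0.63, 0.72

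**Step 4. A yardstick from the trial itself.** The Sample Size Calculation uses d = 0.8, 80% power and a 5% level. A two-sided two-sample t-test needs 25.5 per arm, rounded up to 26, so the stated 52 canines is reproduced, provided that canines are counted as independent. That effect size was set for tooth movement, so for roots it serves only as a scale. With one value per patient, power to detect 0.8 SD is 36% at 9 / 9 and 59% at 16 / 16. In per-canine units, for r from 0 to 1, it runs from 62% to 36% and from 87% to 59%.

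**Step 5. In millimetres, by assumption.** If the per-patient SD of length change were 0.3 to 1.0 mm (assumed; the document gives none), the half-width would be 0.30 to 1.00 mm at 9 / 9 and 0.22 to 0.72 mm at 16 / 16.

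**The case against.** Several points can fairly be made for the authors.

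*The full Results may hold the answer.* The text available stops at the Statistical Analysis section; the full Results, Tables 2 to 4 and the cited root methods are not in it. A root estimate with its interval and numbers may exist there, and an abstract has to be brief. This stands: the document does not show that the root analysis was left undone or unreported. It does not remove the conflict inside the CBCT section, and it does not justify an unqualified statement of no effect.

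*The conclusion may be no wider than the measurement.* A reader might infer that only canine length was read, and that the wording therefore overreaches to roots in general. The methods text does describe only that length, on images with a "field of view (FOV): 6×8 cm limited to the maxilla". But it also names an axial method whose content is not given, and the Abstract uses root condition as its own label for what CBCT assessed. Reading the retracted tooth is a reasonable choice. The mismatch in width is a minor companion point, and it holds only for the text available.

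*The interval point applies to any small trial.* That is true, and it could equally be made about the conclusions on acceleration and pain. The SD is unknown and no threshold for relevant resorption is given, so a reader should not infer that these intervals are clinically too wide. What remains is narrower: a non-significant result does not establish absence.

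*The 36 may simply be right.* Because the text calls those images the ones analysed, 18 pairs is the better-supported reading, and the loose phrase may be the one about every patient. For that reason the fix should not presume which statement is wrong.

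**Conclusion.** The point holds. The CBCT section contradicts itself: scanning every patient implies 64 images, and 36 are stated as the analysis set. As written, the root conclusion appears to rest on 18 of 32 patients (56%), with the arm split and the selection unstated. The 95% half-width for a between-arm difference is about 1.00 SD of a per-patient value at 9 / 9, and 0.72 SD if all 32 were scanned. Neither supports a flat statement that roots were unaffected.

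These sizes rest on an assumed even split of the 18, one averaged value per patient, and an SD that the document does not give.

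Two stronger inferences should be resisted. A reader might suppose that 14 patients were left out because of their results; a planned subset or a miscounted total would explain the figures equally well, and the document does not say. Nor does anything here suggest that the device harms roots. The finding is that absence of harm has not been shown. Root resorption is a side effect outside the null hypothesis, so the comparison of retraction rates is untouched.

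**What to change.** 1. **Records.** Confirm how many patients have a CBCT pair, by arm.
2. **Cone beam Computed Tomography.** Correct whichever is wrong, the statement that every patient was scanned or the count of 36. If only a subset was scanned, say how it was chosen.
3. **Abstract, conclusion.** Replace the root sentence, if the data bear it out, with: *In the N patients with paired CBCT (n1 and n2 per arm), no difference between groups was detected in change of upper canine root-apex-to-cusp length (difference X mm, 95% CI L to U).*
4. **Analysis.** Report the between-arm mean difference with its 95% interval, averaging left and right canines within each patient. The trial is complete and the Trial Design section says that the methodology did not change, so label this post hoc unless it is the analysis that was performed.
5. **Other root readings.** If the cited method or the tables produced any, report them in the same way.

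The cost is a check of the scan records, a few sentences, and a small re-analysis if the existing one treated canines as separate units. No new scans, readings or patients are needed. The drawback is a narrower safety message with a wide interval.
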